LIST OF ABBREVIATIONS AND DEFINITIONS OF TERMS

Abbreviation or Term	Description	
ADA	Anti-drug antibodies	
AE	adverse event	
AESI	adverse event of special interest	
ANCOVA	analysis of covariance	
CHB	chronic hepatitis b	
	Clinical Study Report	
DAIDS	Division of AIDS Table for Grading the Severity of Adult and Pediatric Adverse Events	
DILI	Drug-induced liver injury	
DNA	Deoxyribonucleic acid	
eCRF	Electronic case report form	
EOT	End of treatment	
HBCrAg	Hepatitis B core-related antigen	
HBeAg	Hepatitis B early antigen	
HBsAg	Hepatitis B surface antigen	
IA	interim analysis	
ICH	ICH International Council on Harmonization	
iDMC	iDMC independent Data Monitoring Committee	
IMC	Internal Monitoring Committee	
IMP	P Investigational medicinal product	
IRF	IRF Independent Review Facility	
ISG	Interferon-stimulated genes	
ISR	Injection site reactions	
IxRS	interactive voice/web-based response system	
LFT	Liver function tests	
LLoQ	lower limit of quantification	
MedDRA	Medical Dictionary for Regulatory Activities	
mITT	Modified intent to treat	
NME	New molecular entity	
NUC	Nucleos(t)ide	
PD	pharmacodynamic	
PK	PK pharmacokinetic	
Q4W	Every 4 weeks	
QD	Once a day	
QOD	Once every other day	

QRS	QRS complex	
QT	QT interval	
QTc	QT corrected for heart rate	
QTcF	QT corrected for heart rate using the Fridericia's correction factor	
QW	Once a week	
RNA	Ribonucleic acid	
SAE	serious adverse events	
SAP	Statistical Analysis Plan	
siRNA	Short interfering RNA	
SOC	Scientific Oversight Committee	
TLR7	Toll-like receptor 7	
TND	Target not detected	
MI	Multiple Imputation	
MAR	Missing at Random	

1. INTRODUCTION

This is a Phase II, randomized, adaptive, open-label, multi-arm, multi-center, international, platform study designed to evaluate safety, tolerability, and efficacy of NME combination therapies in CHB participants with preserved liver function and without significant fibrosis/cirrhosis. The platform design allows comparison of multiple new combination therapies against a common control, and introduction of additional treatment arms at later study time points.

This document contains details of the data analysis and handling rules to be used in the analysis of the clinical, pharmacodynamic (PD) and biomarker data from the study WV41073.

1.1 OBJECTIVES AND ENDPOINTS

Table 1 Primary and Secondary Objectives and Corresponding Endpoints

Primary Objective(s)	Corresponding Endpoints
To estimate the effect of NME combination therapies on inducing a functional cure over the control arm.	% participants with HBsAg loss (loss (i.e., HBsAg <0.05 IU/mL) at 24 weeks post-EOT.
Secondary Objective(s) ^a	Corresponding Endpoints
To characterize the efficacy	% participants with HBsAg loss.
profile of NME combination therapies.	% participants with HBsAg seroconversion.
	 % participants with HBeAg loss (baseline HBeAg-positive participants).
	 % participants with HBeAg seroconversion (baseline HBeAg-positive participants).
	 % participants with HBV DNA < lower limit of quantification (LLOQ), <200 IU/mL and <2,000 IU/mL.
 To characterize the PD profile of NME combination therapies. 	 Change from baseline in quantitative HBsAg, anti-HBs, HBeAg, anti-HBe, HBcrAg, HBV RNA, and HBV DNA levels over time.
To characterize the plasma PK profiles of NMEs.	Estimated PK parameters from sparse sampling and population PK models (included below parameters but not limited to)
	Area under the curve (AUC)
	Peak Concentration (Cmax)
	Volume of distribution (Vd)
	Clearance (CL)

		Urir	ne PK
•	To assess the safety and tolerability of NME combination therapies.	•	Incidence, nature and severity of adverse events.
		•	Incidence of laboratory abnormalities based on hematology, clinical chemistry, lipids, thyroid function tests, coagulation, urinalysis test.
		•	ECGs.
		•	Vital signs including blood pressure, pulse rate, respiratory rate and body temperature.
		•	Anti-drug antibodies (ADA) (if applicable)
•	To identify presence of PK/PD relationship.	•	Analyses of PK/PD data.
•	To explore potential effects of ADA on NMEs and/or IMP, as applicable.	•	Relationship between ADA status, PK, safety, PD, and efficacy.
	Exploratory Objective(s)		Corresponding Endpoints
•	To characterize the profile of novel viral response markers.	•	Profiles and changes from baseline of total HBsAg post-dissociation of HBsAg-HBsAb complexes/components of HBsAg and quantitative anti-HBc (IgG or total).
•	To assess the relationship between baseline disease characteristics and efficacy/safety responses.	•	Association between primary and secondary outcomes and HBV genotype (obtained using HBV RNA or DNA sequencing and/or any alternative methodology, and/or from medical records prior to study entry).
•	To assess the association of genetic polymorphisms with the PK profiles of NMEs and/or efficacy/safety primary and secondary endpoints.	•	Genetic association with PK parameters and/or primary and secondary endpoints by clinical genotyping.

Abbreviations: %=percent; AE=adverse event; DNA=deoxyribonucleic acid; EOT=end-of treatment; HBcrAg=hepatitis B core-related antigen; HBeAg=hepatitis B e antigen; HBsAg=hepatitis B surface antigen; HBV=hepatitis B virus; LLOQ=lower limit of quantification; NME=new molecular entity; NUC=nucleos(t)ides; PD=pharmacodynamic; PK=pharmacokinetic; RNA=ribonucleic acid.

1.2 STUDY DESIGN

This study is designed to be adaptive to open additional shorter duration treatment arms or to expand existing treatment arms for NME combination therapies that show promising efficacy outcomes. The platform design also has the flexibility to open new treatment arms to explore different combination regimens or different patient populations pending new submission and HA/EC approval. Based on emerging data and/or company prioritization of assets, treatment arms may be terminated early or not opened for randomization or certain NMEs in the combination treatment arm might be terminated

^a Efficacy and PD endpoints are assessed at every 12-week time point.

while therapy is maintained with the remaining NMEs. The Sponsor will notify the Investigator and HA/EC if the study or certain treatment arms or certain NMEs are placed on hold, or if the Sponsor decides to discontinue certain treatment arms or certain NMEs.

Treatment arms may be staggered relative to other treatment arms in order to increase study efficiency with regards to timely interim data readouts or to reduce the complexity of study conduct. For the first combination, participants will be randomized on Day 1 to an NME combination arm (N=30) or the control arm (N=30) using an adaptive stratified sampling method, stratified at screening HBsAg level (< 1,000 IU/mL, ≥ 1000 IU/mL), with a minimum of 12 participants per arm with a screening HBsAg level of < 1000 IU/mL. For NME combination arms that will be introduced later into the platform study, the allocation ratio of participants to the control arm, will depend on the number of actively enrolling arms with the stipulation that no more than 17% of participants will be randomly allocated to a control arm. Additionally, for subsequent arms the proportion of patients with HBsAg level < 1000 IU/mL, ≥ 1000 IU/mL within each treatment arm, will be maintained as closely as possible to the first combination treatment and the NUC control arm (first set of enrollments).

Due to COVID-19 situation in March - May 2022, as of 31 May 2022 approximately 30-53% of participants in each treatment arm have missed study visits and siRNA drug administration at the site. As a result, a number of participants have consecutive visits missed with a potential impact on the evaluation of the primary endpoint due to incomplete data. To preserve the viability of the study, if the COVID-19 situation continues, or any future COVID-19 outbreaks or any force majeure (e.g. natural disasters, supply chain disruption, outbreak of hostilities etc.,) impacting participants, will lead to additional participants being recruited to the study to ensure that the number of participants per treatment arm with the full dose as per the randomized dose regimen remains approximately 30. The maximum number of additional participants to be recruited will be approximately 30 for each treatment arm.

The treatment period duration will be a maximum of 48 weeks, after which participants will enter a 48-week follow-up period. A shorter treatment duration (12 or 24 weeks) for NME combination arms, and a 48-week response-guided therapy (RGT) arm may be added following planned interim analyses; up to four interim analyses are planned for each treatment arm. Treatment arms that achieve 30% difference, compared to NUC control arm, for HBsAg loss at EOT or at follow-up weeks 12 and 24 (primary endpoint) may be expanded to accrue additional efficacy and safety data and to contribute to Phase 3 design planning as guided by the emerging data, for example, enrichment for

HBeAg positive or HBeAg negative participant populations. An expansion may also be triggered prior to EOT, for a treatment arm that gives an early indication of efficacy. The decision criteria to trigger an expansion arm in this case, will be documented as an appendix to the IMC/Scientific Oversight Committee (SOC) charter.

The total length of the study, from screening of the first participant to the end-of-study is expected to be approximately 3 to 5 years, depending on the number and timing of additional treatments arms that are added to the study.

The study duration for each participant will be approximately 2 years divided as follows:

- Screening period: up to 8 weeks.
- Treatment period: up to 48 weeks.
- Safety follow-up period: 48 weeks.

Table 2 Analysis Timing

The timing of planned interim analyses and RGT below are illustrated based on a 48week treatment duration arm; for arms with shorter treatment duration, the number of the interim analyses as well as the RGT early treatment discontinuations will be adjusted accordingly.

Analysis	Timing of Analysis
First interim analysis	All participants in the study have completed their 12-week visit for a treatment arm or discontinued prematurely
Second interim analysis	All participants in the study have completed their 24-week visit for a treatment arm or discontinued prematurely
Third interim analysis	All participants in the study have completed their 48-week (EOT) visit for a treatment arm or discontinued prematurely
Fourth interim analysis	All participants in the study have completed their follow-up week 12 visit or discontinued prematurely
Primary	All participants in the study have completed their follow-up week 24 visit or discontinued prematurely
Final	The end-of-study for a treatment arm is defined as the date when the last participant completes their follow-up week 48 visit or discontinued prematurely

1.2.1 Treatment Assignment and Blinding

This is an open-label study; however, the specific treatment to be taken by a participant will be assigned using an Interactive Voice/Web Response System IVRS/(IWRS).

Potential selection bias due to the open-label status of this study will be reduced by the use of central randomization. The site will contact the IVRS/IWRS prior to the start of study treatment administration for each participant. The site will record the treatment assignment on the applicable electronic case report form (eCRF), if required.

This study will use an adaptive stratified sampling method, minimization, for randomization. The first participant will be allocated a treatment at random; the treatment allocated to the next participant will be dependent on the characteristics of those participants already enrolled with the aim of minimizing the imbalance within each stratification level (screening HBsAg level < 1,000 IU/mL vs. ≥ 1000 IU/mL). A minimum of 12 participants per arm with a screening HBsAg level of < 1000 IU/mL, is required.

For treatment arms starting at later study time points, the ongoing central randomization to the control arm ensures any potential selection bias is minimized. The subsequent randomization ratio will depend on the number of experimental treatment arms that are open for recruitment with the condition that no more than 1/6th (0%-17%) of the participants will be randomly allocated to the control arm at a given time. Additionally, for subsequent arms the proportion of HBsAg level < 1000 IU/mL or ≥ 1000 IU/mL within each treatment arm will be maintained as closely as possible to the first combination treatment and the NUC control arm (first set of enrollments).

Randomization will also take into account arm-specific exclusion criteria of actively enrolling arms. Participants will be ineligible for a specific arm if they meet any of the exclusion criteria outlined for that arm. The arm-specific exclusion criteria will specifically relate to safety due to the molecule's Mechanism of Action (MOA); therefore, it is not expected to introduce any bias in the efficacy outcome. However, a flexible cap will be added to the other recruiting arm(s) to control the number of participants being randomized to these arms, in order to maintain the element of randomization to the end of the randomization period.

Expansion arm/s (of a treatment arm that show promising efficacy outcomes): if only one expansion arm is open at the time, eligible participants will be enrolled in that arm. If two or more expansion arms are enrolling at one time, a fixed permuted block randomization will be used to allocate participants to arms.

As an additional step to minimize bias, on-treatment virology data (HBV DNA excluded) will not be routinely available to sites, and they will be stored in a restricted data repository for access by the IMC Biometricians. During study conduct, aggregated summaries of data will only be available to the IMC and SOC. However, other members of the Sponsor may have access to aggregated summaries/virology data to assist with decision making, as considered necessary by the IMC.

1.2.2 Independent Review Facility

No Independent Review Facility (IRF) is planned for this study.

1.2.3 Data Monitoring

The IMC will perform periodic safety data review to ensure that continuation of the study does not pose a health hazard to participants, and review the results from the interim analyses to make recommendations about initiating new treatment arms based on predefined criterion.

IMC meetings will be scheduled following each of the planned interim analyses.

Additional review meetings may be scheduled as determined by the IMC. Membership of the IMC will include representatives from Clinical Science (Translational Medicine), Clinical Safety, Biostatistics. If required, additional functional representatives may attend an IMC meeting.

A SOC will act as a consultative body to the Sponsor, providing external expert opinions on the safety data collected during the study. This committee will consist of an external group of at least two CHB therapeutic area experts who will advise the Sponsor on the interpretation of study data.

Data being evaluated by the SOC will include demographic, adverse event, serious adverse event, and relevant laboratory data. SOC may review efficacy data if safety concerns necessitate benefit-risk assessments. The Sponsor will retain all decision-making authority for this study.

Further details on the IMC and SOC, including membership, roles and responsibilities, are provided in the IMC and SOC Charter.

1.2.4 Stratification Factor

The first participant will be allocated a treatment at random; the treatment allocated to the next participant will be dependent on the characteristics of those participants already enrolled with the aim of minimizing the imbalance within each stratification level (screening HBsAg level < 1,000 IU/mL vs. ≥ 1000 IU/mL). A minimum of 12 participants per arm with a screening HBsAg level of < 1000 IU/mL, is required.

For statistical analysis, the actual stratification will be used for analysis (that is based on screening HBsAg level). The stratification based on IxRS data and calculated based on actual data will be listed to compare if any inconsistencies.

2. STATISTICAL HYPOTHESES AND SAMPLE SIZE DETERMINATION

2.1 STATISTICAL HYPOTHESES

As this is an exploratory study, no formal hypothesis testing will be performed.

2.2 SAMPLE SIZE DETERMINATION

Approximately 30 participants will be randomized in each treatment arm. Approximately five replacement participants per arm may be replaced if participants have a dose regimen change or discontinue due to non-safety reasons. This is to ensure that the number of participants per arm of the randomized dose regimen remains close to 30.

In the event of COVID-19 or force majeure events that significantly impact compliance with the randomized dosing regimen, up to 30 additional participants may be enrolled per treatment arm to ensure that the randomized dose regimen remains close to 30. Criteria and the decision to enroll additional participants will be at the Sponsor's discretion.

The overall number of participants in this study will depend on the number of treatment arms that are included, which is not known at present.

The primary endpoint is the proportion of participants with HBsAg loss at 24 weeks post-EOT. Assuming a 3% NUC response rate, a sample size of 30 participants per arm provides 78% power to detect a pairwise 30% difference between a combination treatment arm and the NUC control arm. This is based on a two-treatment arm continuity corrected, two-sided, chi-squared test of equal proportions at a significance level of 5 %.

The sample size of combination treatment arms that achieve 30% delta for HBsAg loss at Week 48 (EOT) or follow-up Week 12 or 24 may be expanded up to approximately 100 participants. An expansion may also be triggered prior to EOT, for a treatment arm that gives an early indication of efficacy. The decision criteria to trigger an expansion arm in this case, will be documented as an appendix to the IMC/SOC charter. The expansion arm may be utilized to increase the precision of the efficacy treatment estimates; exploration of participant subgroups (e.g., baseline HBeAg status) and/or to gain additional safety data prior to Phase 3 clinical trials.

3. ANALYSIS SETS

The participant analysis sets for the purposes of analyses are defined in Table 3.

Table 3 Participant Analysis Sets

Population	Description
Safety	All participants randomized to a treatment regimen who received at least one dose of any drug for their assigned treatment regimen, whether prematurely withdrawn from the study or not, will be included in the safety analysis.
Modified ITT	All participants who were randomized and received at least one dose of each drug for their assigned treatment regimen. Participants will be analyzed according to the treatment arm to which they were randomized.

Pharmacokinetic	Participants will be excluded from the PK analysis population if they significantly violate the inclusion or exclusion criteria, deviate significantly from the protocol, or if data are unavailable or incomplete which may influence the PK analysis. Excluded cases will be documented together with the reason for exclusion. All decisions on exclusions from the analysis will be made prior to database closure.
Immunogenicity	All Participants who had at least one pre- dose (baseline) or at least one post-dose ADA assessment will be included and analyzed according to the treatment they actually received or were allocated to receive,

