Appendix 12 Study Details Specific to siRNA (RO7445482) + TLR7 (RO7020531) + NUC Arm

[figure not shown]
An overview of short interfering RNA (siRNA) + toll-like receptor 7 (TLR7) + nucleos(t)ide NUC treatment arm is shown in Appendix 12-Figure 1.

Participants will receive RO7445482 (also known as DCR-HBVS; 200 mg Q4W) in addition to their background NUC therapy for the 48-week treatment period. RO7020531 (150 mg once every other day [QOD]) will be administered during Weeks 13-24 and Weeks 37-48 (i.e., 2 treatment cycles of 12 weeks' duration each and 42 doses of RO7020531 for each cycle). At the end of the treatment period, participants will continue NUC treatment during the follow-up unless the NUC discontinuation criteria have been met (see Section 6.8).

Approximately 30 participants will be randomized to this treatment arm.

If a 30% delta for HBsAg loss is observed at Week 48 (EOT) or follow-up Weeks 12 or 24 (primary endpoint) the treatment arm may be expanded to accrue additional efficacy and safety data, and to contribute to Phase 3 design planning. If a successful interim analysis is observed at Weeks 12 or 24, shorter treatment duration arms (12 and 24 weeks' duration) and/or a response-guided therapy (RGT) arm may be added.

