Appendix 13 Study Details Specific to siRNA (RO7445482) + PD-L1 LNA (RO7191863) + NUC Arms

An overview of short interfering RNA (siRNA) + programmed death ligand-1 locked nucleic acid (PD-L1 LNA) + nucleos(t)ide (NUC) treatment arms is shown in Appendix 13-Figure 1.

Participants will receive RO7445482 (also known as DCR-HBVS; 200 mg every 4 weeks [Q4W]) and RO7191863 in addition to their background NUC therapy in one of two treatment arms that will run in parallel.

[figure not shown]
- One treatment arm will evaluate a 24-week treatment duration where RO7445482 (200 mg Q4W) will be given during Weeks 1-24 and RO7191863
 will be given during Weeks 13-24.
- A second treatment arm will evaluate a 36-week treatment duration where RO7445482 (200 mg Q4W) will be given during Weeks 1-24 and RO7191863 will be given during Weeks 25-36.

In both treatment arms, participants will receive their background NUC therapy for the duration of study treatment. At the end of the treatment period, participants will continue NUC treatment during the follow-up unless the NUC discontinuation criteria have been met (see Section 6.8).

Approximately 30 participants will be randomized to each treatment arm.

If a 30% delta for hepatitis B surface antigen (HBsAg) loss is observed at end-of-treatment (EOT) or follow-up Weeks 12 or 24 (primary endpoint) the treatment arm may be expanded to accrue additional efficacy and safety data, and to contribute to Phase 3 design planning.

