4.1 GENERAL CONSIDERATIONS

Disposition and protocol deviations listings and summaries will be based on all randomized participants. Analysis of safety will be based on the safety population. Pharmacodynamics and efficacy analysis will be based on the modified intention-to-treat (mITT) population. Pharmacokinetic analysis will be based on PK population. Immunogenicity analysis is based on the immunogenicity population.

For the treatment arms where additional patients have been recruited to proactively mitigate any impact of COVID-19 or force majeure events, the primary analysis will be performed when approximately 30 patients considered evaluable for the primary analysis reach the primary endpoint of Week 24 post EOT. If the primary analysis is positive for an experimental treatment arm, any additional patients that have been recruited to that treatment arm, will continue and be included in the final CSR.

Evaluable patients: A patient from the mITT population will be considered 'evaluable' if no more than two consecutive siRNA missing doses due to non-safety reasons (e.g., COVID-19 disruptions). This is based on the siRNA liver half-life of ~10 weeks.

estimated from ph1 data. Therefore, after two consecutive missing doses the drug left in the liver is expected to be \sim 40%, which was considered adequate as patients would restart dosing so up to 2 missing doses are not expected to have a major impact on the efficacy.

Evaluable patients in mITT population will be used to estimate the primary endpoint/estimand.

Any subject who does not have a virology parameter evaluation during the pre-specified window for 24-week Follow-up visit (either due to missing assessment or due to early withdrawal from the study or study treatment) will be considered as a non-responder. However, if the subject with missing evaluation is a responder both before and after the visit window, then the subject will be categorized as a responder for that visit.

Key definitions:

The following definitions will be used:

Baseline: The baseline value is defined as the last available valid (quantifiable continuous or categorical value), non-missing observation for each participant prior to first study drug administration. Repeat and unscheduled assessments will be included in the derivation of the baseline values.

HBsAq Loss: HBsAg loss refers to a negative/undetectable HBsAg level, HBsAg loss is defined HBsAg levels <0.05 IU/mL.

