4.2 PRIMARY ENDPOINTS/ESTIMANDS ANALYSES

4.2.1 Definition of Primary Endpoint(s)/Estimand(s)

Definition of Primary Endpoint:

The primary endpoint is HBsAg loss (qHBsAg <0.05 IU/mL) at week 24 post EOT.

The primary endpoint is calculated for each treatment arm as:

% participants with HBsAg loss= (Number of participants with HBsAg loss / total number of participants) *100

The percentage of participants with HBsAg loss will analyzed using evaluable patients from the mITT population.

Definition of Primary Estimand:

In line with the Estimands addendum to ICH E9, the primary efficacy estimand is defined as follows-

The difference between proportions of HBsAg loss (qHBsAg <0.05 IU/mL) at week 24 follow-up in virologically suppressed adult CHB participants on established NUC therapy, with preserved liver function and without significant fibrosis/cirrhosis, treated with

^{**} Evaluate numerical and longitudinal data to understand the discrepancy.

^{***} Depending on numerical values, these may be rare cases of double positive (HBsAg and anti-HBs) usually seen from baseline. Seroconversion will need to be interpreted using longitudinal data.

combination therapy* versus NUC, irrespective of adherence to IMP or whether prohibited medication and/or food has been taken.

*treatment and dose levels will vary depending on the combination arm and are specified in the relevant arm specific appendix.

The primary efficacy estimand is described by the following five attributes:

- a) **Population**: Evaluable patients from the mITT population as defined in section 3. These will be CHB adult participants who are virologically suppressed for more than 6 months on established NUC therapy as defined by the inclusion and exclusion criteria listed in Protocol WV41073 section 5.
- **b) Primary Endpoint**: % participants with HBsAg loss (qHBsAg <0.05 IU/ml) at 24 weeks post-EOT.
- c) Population level summary: The difference between proportions of HBsAg loss (qHBsAg <0.05 IU/mL) between NME combination over the control arm at week 24 post-EOT
- **d)** Treatment conditions: Treatment and dose levels will vary depending on combination arms and are specified in the relevant arm specific appendix.
- e) Intercurrent Event (ICE):

Table 5 Intercurrent Events Impacting Primary Analyses:

Intercurrent Events	SDR/ NSDR	Estimand Approach
Participants with dose interruptions or switching dose/frequency	SDR	Treatment Policy

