Withdrawal from study treatment due to any medical condition or AEs/laboratory abnormalities	SDR	Treatment Policy
Investigator or Sponsor determines that treatment discontinuation is in the best interest of the participant.	SDR	Treatment Policy
Withdrawal from study treatment due to participant's withdrawal of consent, pregnancy, non- compliance with study requirement, or lost to follow-up	NSDR	Treatment Policy
Participants who take prohibited medication and food and continue in the study (List of prohibited	SDR	Treatment Policy

medication and food provided in Table 4)		
COVID-19 related ICE A) Systematic disruptions: i) Discontinued study treatment due to covid19 disruptions ii) Discontinued study due to covid19 disruptions iii) Study treatment interruption due to covid19 disruptions iv) Missed dose(s) with potentially major impact on the efficacy due to covid19	NSDR	Treatment Policy
B) COVID-19 infection related ICEs; i) Covid19 infection and concomitant medication ii) Use of the prohibited medicine or therapy iii) Death due to covid19		
Patients who met the NUC d/c criteria at EOT (or in the follow-up period) but did not stop NUC.	SDR	Treatment Policy

SDR- Study Drug Related, NSDR- Non study drug related

A "treatment-policy strategy" will be used accounting for each type of intercurrent event (ICE) as mentioned above. "treatment-policy strategy" where all observed values will be used regardless of the intercurrent event.

Table 6 List of prohibited medication and food

List of prohibited medication-

Systemic immunosuppressive drugs, immunomodulators, cytotoxic or chemotherapeutic agents, radiation therapy.

Systemic high-dose corticosteroids (e.g. >40 mg prednisolone per day) > 7 days or low-dose corticosteroids (e.g. >20 mg prednisolone per day) for > 14 days.

Arm specific prohibited medications

Prohibited food:

For CpAM, any nutrients have been taken during study which modulate activity of CYP enzymes (e.g., grapefruit-, apple-, or Seville orange-containing products).

For TLR7(3), consumption of green tea beverages during the treatment period.

CHB participants who routinely take herbal medicines which may have immunemodulatory effects

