5.4 APPENDIX 4 ANALYSIS DETAILS SPECIFIC TO PD-L1 LNA TREATMENT COMBINATION ARM

PD-L1 LNA treatment combination arm specific analysis are listed in this appendix.

The PD-L1 LNA treatment combination arms as follow:

- One treatment arm will evaluate a 24-week treatment duration where siRNA (200 mg Q4W) will be given during Weeks 1-24 and PDL1-LNA will be given during Weeks 13-24.
- A second treatment arm will evaluate a 36-week treatment duration where siRNA (200 mg Q4W) will be given during Weeks 1-24 and PDL1-LNA will be given during Weeks 25-36.

In both treatment arms, participants will receive their background NUC therapy for the duration of study treatment. At the end of the treatment period, participants will continue NUC treatment during the follow-up unless the NUC discontinuation criteria have been met

The detail analysis of the PBMC and FNA data will be cover in the next version of the statistical analysis plan.

Estimand for PDL1-LNA Treatment Combination:

The difference between proportions of HBsAg loss (qHBsAg <0.05 IU/mL) at week 24 follow-up in virologically suppressed adult CHB participants on established NUC therapy, with preserved liver function and without significant fibrosis/cirrhosis, treated with combination therapies

- 1) siRNA (200mg Q4W)+ PDL1-LNA + NUC, with 24 weeks treatment duration
- 2) siRNA (200mg Q4W)+ PDL1-LNA + NUC, with 36 weeks treatment duration

versus NUC, irrespective of adherence to IMP or whether prohibited medication and/or food has been taken.

The detail analysis of the PBMC and FNA data will be cover in the final version of the statistical analysis plan.

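### In arms 7, 8 and 9 the each-drug mITT rule drops participants who stop before the second drug starts, against the treatment-policy estimand

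*SAP*

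**What the plan says.** SAP Section 3, Table 3 defines modified ITT as "All participants who were randomized and received at least one dose of each drug for their assigned treatment regimen", analysed as randomised; Protocol 9.3, Table 3 is identical. SAP 4.1 bases efficacy on mITT and the primary estimate on its evaluable members. A participant is evaluable with no more than two consecutive siRNA doses missed for non-safety reasons.

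Three arms start their second drug late:

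- Arm 7 (Protocol Appendix 12): TLR7 "will be administered during Weeks 13-24 and Weeks 37-48".
- Arm 8 (SAP 5.4): siRNA "will be given during Weeks 1-24 and PDL1-LNA will be given during Weeks 13-24".
- Arm 9 (Protocol Appendix 13): siRNA "will be given during Weeks 1-24 and RO7191863 will be given during Weeks 25-36"; RO7191863 is the PD-L1 LNA.

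SAP 4.2.1 states the primary estimand "irrespective of adherence to IMP". Its Table 5 lists "Withdrawal from study treatment due to any medical condition or AEs/laboratory abnormalities" among the intercurrent events, together with stops by investigator or sponsor decision and stops for consent, pregnancy, non-compliance or loss to follow-up. All are assigned Treatment Policy, explained as a strategy "where all observed values will be used regardless of the intercurrent event". Under SAP 4.1, a participant without a virology result in the Week 24 window, whether from a missed assessment or "due to early withdrawal from the study or study treatment) will be considered as a non-responder", with an exception for those who respond both before and after the window.

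**The concern.** Membership of the efficacy set depends on something that happens 12 or 24 weeks after randomisation, and only in the experimental arms. A control participant needs only NUC, which is already background therapy. The primary response rate in arms 7 to 9 is therefore conditional on staying on treatment until the second drug, and the control rate is not.

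The plan's own handling of early stopping cannot operate on people outside the set. Treatment policy would use their observed Week 24 result, and the non-responder rule would cover a missing one. Protocol 8.11.3 asks participants who stop treatment but stay in the study to keep attending follow-up, so results can exist and still not enter any efficacy estimate.

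The exclusion may also be related to outcome. Protocol 8.3.8.1 discontinues the NMEs after confirmed virological breakthrough. If that happens before the second drug, a participant with poor viral control leaves the experimental denominator, while a control participant with breakthrough stays in. The rate at stake feeds the 30-point criterion for expanding an arm and informs Phase 3 planning.

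**Working it through.** **The plan's own figure, for context.** SAP 2.2 gives 78% power for 3% versus 33%, 30 per arm, with a continuity-corrected two-sided chi-squared test at 5%.

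- Pooled proportion: (0.03 + 0.33)/2 = 0.18.
- Null SE: √(0.18 × 0.82 × 2/30) = 0.0992.
- Alternative SE: √((0.03 × 0.97 + 0.33 × 0.67)/30) = 0.0913.
- Correction: ½(1/30 + 1/30) = 0.0333.
- Power: Φ((0.30 − 0.0333 − 1.96 × 0.0992)/0.0913) = 78.6%.

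The stated figure is reproduced. The concern is about definitions and does not depend on it.

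**Does any planned efficacy analysis restore these participants?**

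- Primary (SAP 4.2.2): evaluable mITT, so no.
- All-patients sensitivity analysis (SAP 4.2.3): adds unevaluable participants, but still within mITT, so no.
- Multiple-imputation supplementary analysis (SAP 4.2.4): keeps the primary population, so no.
- Completer analysis (SAP 4.2.3): names no set, requires full siRNA dosing and falls under the mITT rule in SAP 4.1, so not clearly, and not for early stoppers in general.

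Only disposition and deviation summaries (all randomised) and safety analyses (any drug taken) clearly include them.

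**Overlap with the evaluability rule.** The SAP does not say whether siRNA doses after a permanent stop count as missed. Suppose they do. In arms 8 and 9 siRNA is given at Weeks 1, 5, 9, 13, 17 and 21.

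| Last siRNA dose | Later doses missed | Evaluable if the stop is non-safety? |
|---|---|---|
| Week 9 | 3 (Weeks 13, 17, 21) | No |
| Week 13 | 2 | Yes |
| Week 17 | 1 | Yes |
| Week 21 | 0 | Yes |

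In arm 8 a non-safety stop before Week 13 is already removed. The same holds in arm 7, where all siRNA doses from Week 13 to the end of treatment are missed. In the primary set the each-drug rule then adds two groups: safety-related stops in arms 7 to 9, and arm 9 stops after the Week 13 siRNA dose. An arm 9 participant can receive all six siRNA doses and still be excluded. In the all-patients analysis the rule removes every such early stop, whatever the reason. A temporary interruption does not matter if the second drug is later given.

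**Size.** The number stopping early, k, is not in the documents; 1 to 5 of 30 is assumed. If all k are non-responders, the rate is multiplied by 30/(30 − k), which is 1.03 for k = 1 and 1.20 for k = 5. With 10 responders among 30:

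- k = 0: 10/30 = 33.3%
- k = 1: 10/29 = 34.5%
- k = 3: 10/27 = 37.0%
- k = 5: 10/25 = 40.0%

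Threshold example, crude difference against 1/30 in control: 9/30 − 1/30 = 26.7 points; 9/27 − 1/30 = 30.0 points. Against the planned 3% the figures are 27.0 and 30.3.

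If three excluded participants are replaced, the comparison is 10/33 = 30.3% with them and 10/30 = 33.3% without. If one of three excluded is a responder, 10/30 becomes 9/27 = 33.3%, unchanged.

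**The case against.** The best counter-argument is that the effect is probably small and the conflict partly one of wording. The estimand's population attribute is itself evaluable mITT, so Table 5 can be read as operating inside that set. Before the second drug these participants receive only siRNA and NUC, and the interim Phase 1 data in Protocol A13.2 report no adverse events leading to discontinuation of siRNA. Safety stops in the first 12 weeks may therefore be few, and many non-safety stops are removed by the evaluability rule anyway. The threshold example is chosen: three excluded, none a responder, a control of exactly 30, and a crude rather than CMH-weighted difference. Expansion is at the sponsor's discretion, and the study does no formal testing. Individual ALT and virology profiles are planned among the safety displays, so these HBsAg courses would be seen.

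Much of this stands as a limit on size. For arms 7 and 8 in the primary set, 3 to 5 excluded is not a likely central case. It does not remove the point. A population that conditions on reaching the second drug undoes a strategy that is meant to disregard stopping treatment. Individual plots are not an efficacy estimate. Arm 9 leaves a 24-week window in which the evaluability rule catches only part of the stops.

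**Conclusion.** The concern holds. In arms 7, 8 and 9 the mITT definition makes a one-sided exclusion after randomisation that conflicts with the treatment-policy estimand, and no planned efficacy analysis clearly shows its effect. Arm 9 is the most exposed.

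The size cannot be computed from the documents. Under the assumed 1 to 5 exclusions of 30, all non-responders, a 33.3% rate is overstated by 1.1 to 6.7 percentage points (34.5% to 40.0% before rounding). The direction is upwards only if those excluded respond less often than those kept; otherwise the rate is unchanged or biased downwards. The point should be fixed because the rate enters the 30-point expansion decision and the correction is cheap.

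**What to change.** In SAP Table 3 and Protocol Table 3, define mITT as everyone randomised who took at least one dose of any component of the assigned regimen, analysed as randomised. The Safety row of the same table already uses an any-drug criterion. Use the observed Week 24 follow-up result where there is one and the existing non-responder rule otherwise. Keep the each-drug set as a named sensitivity analysis.

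In SAP 4.1, state that the evaluability filter still applies to the primary set, and whether siRNA doses after a permanent stop count as missed. It would also help to say from which end-of-treatment date Week 24 is counted for early stoppers. The all-patients analysis on the revised mITT then gives an estimate with neither exclusion.

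The cost is one sentence in each table and a short clarification in SAP 4.1, with no new data or participants. The reported rate in arms 7 to 9 may be slightly lower. Because the evaluability filter remains, this change alone does not make the primary analysis a full randomised comparison.
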